The signature of the investigator below constitutes approval of this protocol and provides the necessary assurances that this Outcomes Study will be conducted according to Good Clinical Practices and to all stipulations, clinically and administratively, as stated in the protocol, including all statements as to confidentiality.

It is agreed that the protocol contains all necessary information required to conduct the Outcomes Study as outlined in the protocol.

PRINCIPAL INVESTIGATOR:

Print Name

Signature

Date

Table of Contents

Sponsor Protocol Approval Page	2
Investigator Protocol Approval Page	3
Table of Contents	4
Study Summary	5
Introduction (1)	6
Background (1.1)	6
Device Description (1.2)	6
Purpose of the Study (2)	7
Study Design (3)	7
Study Hypothesis (3.1)	7
Study Description (3.2)	7
Primary Outcome (3.3)	7
Secondary Outcomes (3.4)	7
Study Population (3.5)	7
Sample Size Justification (3.6)	8
Proposed Study Site List and Justification (3.7)	8
Subject Eligibility Criteria (3.8)	9
Inclusion Criteria (3.9)	9
Exclusion Criteria (3.10)	10
Study Procedure (4)	10
Subject Chart Review (4.1)	10
Data Collection Procedure (4.2)	10
Data to be Collected (4.3)	11
Data Management Plan (4.4)	13
Monitoring Plan (4.5)	13
Adverse Events (5)	13
Subject Safety (5.1)	14
Mitigation of Risks (5.2)	14
Image and Data Analysis (6)	15
Radiographic Fusion Assessment (6.1)	15
Data Analysis (6.2)	15
Ethical and Regulatory Requirements (7)	16
Code of Conduct (7.1)	16
Subject Confidentiality (7.2)	16
Retention of Records by Investigator (7.3)	16
References (8)	16

Integrity Implants Study Summary

Study Title:	Transforaminal/Posterior Lumbar Interbody Fusion with the FlareHawk® Expandable Interbody Fusion Device: A Retrospective Chart Review Study
Study Design:	Retrospective study – chart review
Study Purpose:	To evaluate the clinical outcomes of patients undergoing transforaminal or posterior lumbar interbody fusion (TLIF or PLIF) procedures using a FlareHawk expandable interbody fusion cage
Study Population:	Patients who underwent 1 or 2 contiguous level TLIF or PLIF procedure with the FlareHawk expandable interbody fusion cage. A total of at least 100 patients from at least three sites will be enrolled based on inclusion/exclusion criteria.
Minimum Follow-up:	12 months +/- 3 months
Primary Outcome:	Proportion of subjects with radiographic arthrodesis at 12 months +/- 3 months
Secondary Outcomes:	
• Change in VAS Leg pain from preoperative baseline to 12 months +/- 3 months• Change in VAS Back pain from preoperative baseline to 12 months +/- 3 months• Change in Oswestry Disability Index (ODI) from preoperative baseline to 12 months +/- 3 months• Other intra-operative or post-operative adverse events

1. Introduction

1.1 Background

Degenerative disc disease (DDD) of the lumbar spine is commonly defined by discogenic pain with degeneration of the disc confirmed by patient symptom history (e.g. back and lower extremity pain) and radiographic findings (e.g. disc space collapse and stenosis). DDD is sometimes accompanied by spondylolisthesis (vertebral “slipping”) of varying extent, with Grade I being the most mild. The most common therapies available for lumbar DDD are conservative care (e.g. injections, chiropractic manipulations), decompression without fusion, posterolateral fusion (PLF), or lumbar interbody fusion (LIF). With more than 6 months of failed conservative care, patients may be indicated for surgical intervention and LIF is often regarded as the mainstay of surgical care for degenerative disc disease [Noshchenko et al. 2015; Yavin et al. 2017]. Transforaminal lumbar interbody fusion (TLIF) and posterior lumbar interbody fusion (PLIF) are two variants of LIF surgery that utilize a posterior approach.

More recently, expandable interbody cages have been introduced for use in TLIF or PLIF procedures. Expandable cages, in general, have the potential advantage of facilitating more minimally invasive surgery while achieving substantial disc height and neuroforaminal height restoration as well as lordosis. Designs that expand in the transverse plane (medially-laterally) may also reduce subsidence risk due to their larger footprint. The FlareHawk expandable interbody fusion cage offers a simple expansion mechanism to achieve biplanar (cranial-caudal and medial-lateral) expansion in situ. This device is currently FDA-cleared in the United States and has been adopted into standard clinical practice beginning in August 2016, with over 3800 devices implanted to date. This study is a retrospective chart review to assess the performance and safety of the FlareHawk expandable cage under its intended use.

1.2 Device Description

The Integrity Implants FlareHawk Interbody Fusion System is an expandable lumbar intervertebral body fusion device intended for use in the lumbosacral spine from L2-S1 and is intended for intervertebral lumbar fusion. The FlareHawk implant consists of a Shell and a Shim component that are offered in a range of sizes to accommodate variation in patient anatomy. The Shell component is a rectangular frame with struts on all four sides that allow for insertion into the intervertebral body space in a non-expanded form, and subsequent expansion following the insertion of the Shim component. The Shim component has a tapered front end that inserts into and expands the Shell component to the desired vertical and horizontal dimensions. When fully inserted, the Shim locks within the Shell to provide structural stability for interbody fusion. An integrated “Core” in the Shell serves to anchor the delivery instrument during Shim insertion. Protrusions on the superior and inferior surfaces of the implant grip the adjacent vertebral endplates to resist expulsion. The FlareHawk implant is to be filled with autogenous and/or allogenic bone graft composed of cancellous and/or corticocancellous bone. Once implanted, the FlareHawk

implant is designed to restore intervertebral disc height, provide anterior column support and maintain structural stability of the motion segment to facilitate intervertebral body fusion.

2. Purpose of the Study:

The purpose of this study is to evaluate the clinical outcomes of patients who have undergone a TLIF or PLIF procedure with a FlareHawk expandable interbody fusion cage(s) to assess the device's performance and safety when used in accordance with its intended use.

3. Study Design

3.1 Study Hypothesis:

The primary hypothesis is that study subjects who received the FlareHawk expandable cage(s) through a TLIF or PLIF procedure experienced fusion by 12 months (+/- 3 mo) follow-up, with improvements in clinical outcomes related to pain and/or disability compared to pre-operative scores. Further, the subjects are hypothesized to have not experienced any unforeseen device- or procedure-related adverse events.

3.2 Study Description:

This is a retrospective clinical study (chart review) of patients who have previously undergone TLIF or PLIF surgery with the FlareHawk expandable interbody fusion cage at one or two contiguous levels.

3.3 Primary Outcome:

Proportion of subjects with radiographic arthrodesis at 12 months +/- 3 months as determined using plain radiographic images with assessment based on the Bridwell-Lenke grading system [Bridwell and Lenke et al, 1995].

3.4 Secondary Outcomes:

- Change in VAS Leg from preoperative baseline to 12 months +/- 3 months
- Change in VAS Back from preoperative baseline to 12 months +/- 3 months
- Change in Oswestry Disability Index (ODI) from baseline to 12 months +/- 3 months
- Intra-operative and post-operative adverse events

3.5 Study Population:

A total of at least 100 patients from at least three sites will be enrolled based on inclusion/exclusion criteria. Homogeneity of data collection and treatment procedures will be ensured prior to combining data from multiple sites. The retrospective chart review will include the full consecutive series of patients who received TLIF or PLIF surgery using the FlareHawk expandable interbody fusion cage between December 1, 2017, and May 31, 2018. Subjects from that consecutive series will be included in the study based on the pre-defined inclusion and exclusion

criteria, detailed below. If at least 100 patients are not included after screening through the pre-defined inclusion / exclusion criteria, the date range will be extended, and the full consecutive series of patients within the new date range will be considered for inclusion. The date range will be extended, as necessary, until at least 100 patients are included. All subjects will have been diagnosed with degenerative disc disease of the lumbar spine that required lumbar interbody fusion procedure at one or two levels as per the opinion of the treating surgeon. All subjects who meet the inclusion criteria and do not meet any of the exclusion criteria will be included in the study.

Two versions of the device have been on the market recently. The “Split Shim” version was introduced to the market in January 2018. This version supersedes the previous version, “Version B”, which has been on the market since January 2017. These two versions of the device have subtle differences and are equivalent from the clinical, technical, and biological perspective, and are expected to demonstrate equivalent safety and performance. Therefore, data will be collected from patients treated with either version of the device. A subgroup analysis will be performed to confirm poolability of the data.

3.6 Sample Size Justification

The primary outcome of this study, radiographic arthrodesis, is commonly observed in approximately 80-100% of study subjects for TLIF/PLIF surgeries [FlareHawk CER-00001 Rev C]. With 100 subjects included, if an 88% fusion rate is observed, the 95% confidence interval¹ for fusion success will be 80.2%-93.0%, placing the performance results within the anticipated range. Further, the inclusion of at least 100 subjects will enable the likely detection of adverse events that have a probability of occurrence of at least 1.6%, assuming a power of 80% [MedDev 2.7.1, rev 4]. This detection rate is adequate for this device and study based on the severity and frequency of anticipated adverse events associated with the FlareHawk device [FlareHawk CER-00001 Rev C]. The target sample size for inclusion will be 118 patients, assuming that up to 15% will not have data at the 12 months follow-up, yielding at least 100 patients with data.

[name] is a private practice orthopedic surgeon. He represents the majority of orthopedic spine surgeons in the community with an emphasis on degenerative spine and will does some basic deformity. [name] uses a mini-open approach for his TLIF insertion, and a specialized retractor for visualization. [name] has taught many US courses and is recognized in the Savannah community as one of the top local physicians.

3.8 Subject Eligibility Criteria:

The principal investigator at each site is responsible for verifying that study subjects meet all inclusion/exclusion criteria.

3.9 Inclusion Criteria:

Subjects must meet all of the inclusion criteria to be included in this study.

To be a part of this study, the subject must:

1. Have been at least 18 years of age and skeletally mature at the time of surgery
2. Have had clinical and radiological evidence of degenerative disc disease of the lumbar spine

3. Have been treated with PLIF or TLIF surgery using the FlareHawk expandable interbody cage(s) at 1 or 2 contiguous levels from L2 to S1
4. Have been treated using the FlareHawk expandable interbody fusion cage, according to the approved labeling, between December 1, 2017, and May 31, 2018

3.10 Exclusion criteria:

Subjects must not meet any of the following exclusion criteria to be included in the study:

1. Have a history of fusion surgery at the study level(s) prior to treatment with the FlareHawk device(s)
2. Have had spondylolisthesis unable to be reduced to grade 1 as part of the surgical procedure
3. Have had surgery with the FlareHawk device(s) at more than 2 levels
4. Have had surgery with the FlareHawk device(s) at levels outside the range of L2 to S1
5. Have been treated with any bone grafting material other than autogenous or allogenic bone graft in the FlareHawk device(s) and surrounding disc space
6. Have any contraindications listed in the approved labeling

4. Study Procedure

4.1 Subject Chart Review:

The chart reviews will be conducted by the study investigator or a trained study coordinator at each site. Records from all patients who underwent PLIF or TLIF surgery with the FlareHawk expandable cage between December 1, 2017, and May 31, 2018, will be identified for further screening according to the inclusion and exclusion criteria. Those subjects meeting all of the inclusion criteria and none of the exclusion criteria will be included for data collection. If there are not at least 118 patients included for data collection, the date range will be extended. If there are not at least 100 patients included with follow-up data at 12 (+/- 3) months, the date range will be extended.

4.2 Data Collection Procedure:

All data will be collected on de-identified case report forms (CRF) located at the participating site. Each subject will be identified only by a number which is generated at each site. No PHI will be available or seen by any study personnel with the exception of the investigator or his designee. All printed study records at the site will be maintained in a secure location. The data will be maintained by the investigator and information collected will be available to the study sponsor.

Source Documents

Source data is all information, original records of clinical findings, observations, or other activities in a clinical trial necessary for the reconstruction and evaluation of the trial. Source data are contained in source documents.

Examples of these original documents, and data records include: hospital records, clinical and office charts, laboratory notes, subjects' diaries or evaluation checklists, copies or transcriptions certified after verification as being accurate and complete, and X-rays.

Case Report Forms

The study case report form (CRF) is the primary data collection instrument for the study. All data requested on the CRF must be recorded. All missing data must be explained. If a space on the CRF is left blank because the procedure was not done or the question was not asked, write "N/D". If the item is not applicable to the individual case, write "N/A". All entries should be printed legibly in black ink. If any entry error has been made, to correct such an error, draw a single straight line through the incorrect entry and enter the correct data above it. All such changes must be initialed and dated. DO NOT ERASE OR WHITE OUT ERRORS. For clarification of illegible or uncertain entries, print the clarification above the item, then initial and date it. The investigator will be responsible for maintaining adequate, accurate CRFs to guarantee the proper interpretation of the data.

4.3 Data to be Collected:

After confirming inclusion in the study based on the above inclusion and exclusion criteria, data collection from the subject record will include the following, as available:

1. Demographics:

- Age
- Gender at birth
- Diagnosis
- BMI
- Co-morbid conditions
 - Hypertension
 - Diabetes
 - Obesity (BMI \geq 30)
 - Hypercholesterolemia
 - Coronary Heart Disease
 - Hypothyroidism
 - Active or history of cancer
 - Other
- Smoking Status

2. Operative data:
 - Date of Surgery
 - Surgical level(s)
 - Description of all implants and graft materials used, including supplemental fixation if described
 - PLIF or TLIF approach
 - Open, mini-open, or minimally invasive procedure
 - Estimated blood loss
 - Length of surgery
 - Fluoroscopic exposure time
 - Intraoperative device- or procedure-related adverse events
 - Device component breakage/fracture
 - Device malfunction
 - Dural tear/injury
 - Nerve root injury
 - Device-related delay of surgery
 - Retained foreign body
 - Other
 - Length of hospitalization
3. Patient reported outcomes surveys at preoperative baseline and each follow-up:
 - Visual Analog Scale (VAS) back and/or leg – Self Administered Questionnaire
 - Oswestry Disability Index (ODI) - Self Administered Questionnaire
4. Radiographs:
 - Intraoperative post-implantation Lateral and AP X-rays of the lumbar spine
 - 12 months (+/- 3 months) follow-up Lateral, AP, and Flexion-Extension X-rays of the lumbar spine
5. Post-operative device- or procedure-related adverse events
 - Infection
 - Donor site pain
 - Complex Regional Pain Syndrome
 - Urinary retention/difficulty
 - Ipsilateral or Contralateral radiculopathy
 - Device component fracture

- Device or device component migration/retropulsion
- Device complication (e.g. loss of expansion)
- Device subsidence
- Loss of fixation
- Non-union
- Vertebral fracture
- Adjacent segment disease
- Other

4.4 Data Management Plan:

Data processing and management will be carried out in accordance with the study-specific data processing plan. The data will be verified per the Monitoring Plan and CRFs will be collected by the clinical research associate (CRA) upon completion. Data will be entered into a password protected and encrypted database by the CRA and will be verified by double data entry.

Any missing, implausible or inconsistent recordings will be referred back to the Investigator using a data query form and will be documented for each individual subject. Responses from the Investigator will be reviewed and updated in the Database. This process will be repeated until no further discrepancies are found. The data will be then be declared as clean.

4.5 Monitoring Plan:

This study will be monitored according to the monitoring plan. The investigator and study staff will allocate adequate time for such monitoring activities. The investigator will also ensure that the monitor or other compliance or quality assurance reviewer is given access to all the above noted study-related documents. A remote pre-qualification assessment will be completed with the investigator and study staff to ensure they are experienced and available to conduct the study. Selected sites will participate in an initiation visit and will be trained on the study protocol and study related responsibilities. Interim remote or onsite monitoring visits will be conducted for cause and one on-site visit will occur once the study site has completed the CRFs, so that the CRA can verify the collected data to the source documents.

5. Adverse Events:

Per EN ISO 14155, an adverse event is defined as any untoward medical occurrence, unintended disease or injury, or untoward clinical signs (including abnormal laboratory findings) in subjects, users or other persons, whether or not related to the investigational medical device as any undesirable deviation from the subject's baseline condition

to include all new conditions or symptoms, or worsening of the pre-existing condition or symptoms regardless of the cause. This definition includes events related to the procedures involved.

The intensity of the adverse event will be determined by the investigator using the following definitions established by the World Health Organization and not necessarily the subject's interpretation:

None: patient outcome is not symptomatic, or no symptoms detected and no treatment is required.

Mild: patient outcome is symptomatic, symptoms are mild, loss of function or harm is minimal or intermediate but short term, and no or minimal intervention (e.g., extra observation, investigation, review or minor treatment) is required.

Moderate: patient outcome is symptomatic, requiring intervention (e.g., additional operative procedure; additional therapeutic treatment), an increased length of stay, or causing permanent or long-term harm or loss of function.

Severe: patient outcome is symptomatic, requiring life-saving intervention or major surgical/medical intervention, shortening life expectancy or causing major permanent or long-term harm or loss of function

Death: on balance of probabilities, death was caused or brought forward in the short term by the incident.

The relationship of the AE to the implant or surgical procedure is determined according to the following definitions:

Device related: The AE can be reasonably associated with the presence or performance of the device and follows a reasonable temporal sequence to the device implant

Procedure related: The AE has been established as a potential risk or complication associated with any type of spinal surgical procedure and not specific to the receipt of the device.

Not related: The AE has no temporal sequence from the receipt of the device or it can be explained by other factors, including underlying disease, concomitant medication or concurrent treatment. This also includes events associated with general surgical procedures (e.g. anesthesia reactions).

5.1 Subject Safety:

The expandable cage used in this study is currently used in standard of care procedures for these lumbar spine disorders. No experimental devices or products were used in this study and all patients were treated according to the standard practices of the study investigators.

5.2 Mitigation of Risks:

This is a retrospective chart review that does not introduce any additional risks to the patient.

6. Image and Data Analysis

6.1 Radiographic Fusion Assessment:

Radiographs will be evaluated by up to three reviewers (two primary reviewers and an adjudicator, as necessary, to evaluate any contradicting reviews by the primary reviewers). Reviewers will be 3rd party board-certified orthopedic surgeons, neurosurgeons, or radiologists.

Fusion status will be determined according to the Bridwell-Lenke grading system [Bridwell and Lenke et al, 1995], with grades 1-2 accepted as “Fused” and grades 3-4 accepted as “Not Fused”:

- Grade 1: Fused with remodeling and trabeculae present
- Grade 2: Graft intact, not fully remodeled and incorporated, but no lucency present
- Grade 3: Graft intact, potential lucency present at top and bottom of graft
- Grade 4: Fusion absent with collapse/resorption of the graft

6.2 Data Analysis:

Primary outcome:

The proportion of levels achieving arthrodesis at 12 months (+/- 3 months) will be summarized as a percentage and 95% confidence interval, based on the Wilson score method for binomial confidence intervals.

Secondary outcomes:

Continuous variables, such as baseline demographics and change in patient-reported outcomes from preoperative baseline to 12 months, will be summarized using mean, standard deviation, minimum and maximum values. Paired t-test or a non-parametric equivalent (if data does not satisfy assumptions of normality) will be used to determine if changes in VAS or ODI scores are statistically significant from preoperative baseline to 12 months (+/- 3 months) follow-up. Responder analyses for changes in patient-reported outcomes at 12 months (+/- 3 months) will be conducted using minimum clinically important differences (MCID). Significant clinical improvements from preoperative baseline to 12 months (+/- 3 months) follow-up will be determined on a per-patient basis using the following MCID values:

- Improvement in ODI \geq 10 points [Ostelo et al. 2008]
- Improvement in VAS leg pain \geq 15 points [Ostelo et al. 2008]
- Improvement in VAS back pain \geq 15 points [Ostelo et al. 2008]

The proportion of patients with improvements exceeding the MCID values will be summarized as a percentage and 95% confidence interval.

Sub-group analyses will be performed based on the implant version (split-shim vs. “Version B”), history of previous surgery at the index level, patient co-morbidities, and demographic variables.

For any adverse events, the observed rate of each type of event will be summarized as a percentage with the 95% confidence interval and compared with rates observed in the literature describing the current state of the art with other PLIF and TLIF interbody cages.

7. Ethical and Regulatory Requirements:

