(Open to Close)Estimated Blood Loss: cc./ml.Length of Hospitalization: daysFluoroscopic Exposure Time: min.**TYPE OF PROCEDURE**Operative Procedure: Open Mini-open Minimally Invasive Operative Approach: PLIF TLIF Number of Levels: One Two Surgery Levels: L2-L3 L3-L4 L4-L5 L5-S1 **IMPLANT(S) USED****Implant #1**

Shell Catalog # _____

Shim Catalog # _____

Shell Lot # _____

Shim Lot # _____

Implant #2NA

Shell Catalog # _____

Shim Catalog # _____

Shell Lot # _____

Shim Lot # _____

Implant #3NA

Shell Catalog # _____

Shim Catalog # _____

Shell Lot # _____

Shim Lot # _____

Implant #4NA

Shell Catalog # _____

Shim Catalog # _____

Shell Lot # _____

Shim Lot # _____

GRAFT MATERIALGraft Materials Used: Allograft Autograft Mix of Allograft/Autograft

Clinical Site Number:

Subject Number:

Case Report Form
Integrity Implants FlareHawk® Study
Surgery – Visit 2

SUPPLEMENTAL FIXATION

Supplemental Fixation Used (check one): Unilateral Bilateral

Description of Construct: _____

ADVERSE EVENTS (AEs)

Did any intra-operative adverse events occur? Yes No

If "Yes", add adverse event to **Intra-Operative AE Log**.

DELAY OF SURGERY

Device Related Delay of Surgery: Yes No

If yes, how many minutes? min.

If yes, cause of delay? _____

INSTRUMENTATION

Were there any reported issues with instrument(s)? Yes No

If yes, please provide the catalog and lot number below as well as the description of the issue with the instrument(s):

Catalog # _____ Description of issue: _____

Lot # _____

Not Recorded

Clinical Site Number:

Subject Number:

Case Report Form
Integrity Implants FlareHawk® Study
Surgery – Visit 2

RADIOGRAPHS

Are intra-operative, post-implantation X-rays available on CD? Yes No

X-ray views taken (*check those that apply*): AP Lateral

If X-rays are available, has the CD been provided to the evaluators? Yes No

ADDITIONAL COMMENTS

Please add any other pertinent information regarding the surgical procedure, the device/instruments or any safety concerns:

Clinical Site Number:

Subject Number:

Case Report Form
Integrity Implants FlareHawk® Study
Follow-up – Visit 3

Page 1 of 3

VISIT 3 – 12 MONTHS (+/- 3MONTHS)

DATE OF VISIT: / /
MM DD YYYY

RADIOGRAPHS

Are 12-month X-rays available on CD? Yes No

X-ray views taken (check those that apply): AP Lateral Flexion/Extension

If X-rays are available, has the CD been provided to the evaluators? Yes No

ADVERSE EVENTS (AEs)

Did any post-operative adverse events occur? Yes No

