Please complete all columns below if additional Adverse Events are recorded.

Other Adverse Events (Describe event below)	Onset Date MM/DD/YYYY	Resolution Date MM/DD/YYYY	Severity 1- None 2- Mild 3- Moderate 4- Severe 5- Death	Relatedness 1- Device related 2- Procedure related 3- Not related	Action Taken 1- None 2- Medication/ Therapy 3- Revision Surgery 4- Additional Surgery 5- Other	Outcomes 1- Resolved 2- Ongoing at 12-month (+/- 3 month) Follow-up 3- Unknown
	/ /	/ /				
	/ /	/ /				
	/ /	/ /				
	/ /	/ /				
	/ /	/ /				

Clinical Site Number: Subject Number:

Case Report Form
Integrity Implants FlareHawk® Study
Radiographic Reviewer

CRF TO BE COMPLETED BY RADIOGRAPHIC REVIEWER ONLYDATE OF X-RAY: / /
MM DD YYYY**RADIOGRAPHS**X-ray views evaluated (check all that apply): AP Lateral Flexion/Extension **RADIOGRAPHS**

Using the Bridwell-Lenke grading system, what is the X-ray fusion status at L2 - L3?	Grade 1	
	Grade 2	
	Grade 3	
	Grade 4	
NA – Subject not implanted with FlareHawk device at L2-L3		

Using the Bridwell-Lenke grading system, what is the X-ray fusion status at L3 – L4?	Grade 1	
	Grade 2	
	Grade 3	
	Grade 4	
NA – Subject not implanted with FlareHawk device at L3-L4		

Using the Bridwell-Lenke grading system, what is the X-ray fusion status at L4 – L5?	Grade 1	
	Grade 2	
	Grade 3	
	Grade 4	
NA – Subject not implanted with FlareHawk device at L4-L5		

Using the Bridwell-Lenke grading system, what is the X-ray fusion status at L5- S1?	Grade 1	
	Grade 2	
	Grade 3	
	Grade 4	
NA – Subject not implanted with FlareHawk device at L5-S1		

Was any magnification adjustment used by the radiographic reviewer to grade fusion status? Yes No

If "Yes", describe below: _____

APPROVAL

Reviewer Signature: _____

Date: _____

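### Film-visible device events (subsidence, migration, loss of expansion and similar) are counted only from site charts, while the third-party readers who are to receive the films grade fusion alone, so the reported rates may be too low

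*Combined protocol and SAP*

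**What the plan says.** **Films.** Attachment A section 4.3, item 4, lists "Intraoperative post-implantation Lateral and AP X-rays of the lumbar spine" and "12 months (+/- 3 months) follow-up Lateral, AP, and Flexion-Extension X-rays of the lumbar spine". Everything in section 4.3 is taken from the subject record as far as it is available. The Surgery (Visit 2) form asks "Are intra-operative, post-implantation X-rays available on CD", and both that form and the Visit 3 form go on to ask "If X-rays are available, has the CD been provided to the evaluators".

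**Readers.** Section 6.1 provides two main readers and a third to settle disagreements: "Reviewers will be 3rd party board-certified orthopedic surgeons, neurosurgeons, or radiologists". Their stated task is the Bridwell-Lenke grade, with grades 1-2 fused and 3-4 not fused. The Radiographic Reviewer form has one X-ray date, the views read, a grade for each level, and the question "Was any magnification adjustment used by the radiographic reviewer to grade fusion status". It has no field for device position or integrity.

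**Events.** Section 4.3, item 5, and the Post-Operative Adverse Event Log list "Device or device component migration/retropulsion", subsidence, loss of expansion, component fracture, loss of fixation and non-union. Under section 4.1 the site investigator or coordinator does the chart review. The log offers Yes or No for each event and one box for no events recorded. The VAS, ODI and smoking fields have a Not Recorded option; the listed events do not.

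**Use.** Section 6.2 (and 9.2 of the main protocol) reports each event type as a percentage with a 95% interval and compares it with published rates for other cages.

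**The concern.** Subsidence, migration and loss of expansion are found mainly by comparing a film taken just after implantation with a later one. The plan gathers both films and has independent specialists to read them, yet no visible analysis uses the intra-operative film. These events enter the data only if someone noted them in routine care and the site then abstracts the note. A finding that caused no symptoms and was never written down becomes a No and counts in the rate as a true negative.

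Safety is half of the study's purpose and adverse events are a secondary outcome. A low charted rate could be read as good device performance when it partly reflects how hard anyone looked. Subsidence deserves particular care because section 1.1 says that cages expanding sideways "may also reduce subsidence risk due to their larger footprint".

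Non-union has a related problem. The site records it from the chart, while the readers separately classify grades 3-4 as not fused. Nothing visible links the two, so two different non-fusion rates could be reported for the same patients without explanation.

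**Working it through.** **1. The plan's own figures (section 3.6).** The chance of at least one event in n = 100 at rate p is 1 - (1 - p)^100.
- At p = 1.6%: 1 - 0.984^100 = 0.8007. The rate giving exactly 80% is 1 - 0.2^(1/100) = 1.597%. The stated 1.6% at 80% reproduces.
- The Wilson 95% interval for 88/100 is 80.2% to 93.0%, as stated.
- 100/0.85 = 117.6, rounded up to 118, as stated.

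**2. What the 1.6% figure assumes.** It counts every event that occurs as recorded. Let s be the share of true events found in the chart. The documents do not give s, so it is varied here, and false positives are ignored. The chance of recording at least one event is 1 - (1 - 0.016s)^100, and the true rate detectable with 80% probability is about 1.597%/s.

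| s (assumed) | Chance of recording a 1.6% event | True rate detectable at 80% |
|---|---|---|
| 100% | 80% | 1.6% |
| 90% | 77% | 1.8% |
| 75% | 70% | 2.1% |
| 50% | 55% | 3.2% |
| 25% | 33% | 6.4% |

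**3. Effect on a reported rate.** Assume a true film-visible rate of 10% in 100 patients. The expected observed rate is 10% x s. The plan names the Wilson method only for the primary outcome; it is used here for event rates too: [p + z²/2n ± z√(p(1-p)/n + z²/4n²)] / (1 + z²/n), with z = 1.96.

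| s (assumed) | Observed | Wilson 95% interval | Contains 10%? |
|---|---|---|---|
| 30% | 3/100 | 1.0% to 8.5% | No |
| 50% | 5/100 | 2.2% to 11.2% | Yes |
| 70% | 7/100 | 3.4% to 13.7% | Yes |

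One interval at the expected count does not show how often the method would fail. Summing over all binomial outcomes, the chance that the nominal 95% interval contains the true rate is:

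| True rate (assumed) | s = 100% | s = 75% | s = 50% | s = 25% |
|---|---|---|---|---|
| 10% | 94% | 88% | 56% | 11% |
| 5% | 97% | 97% | 92% | 72% |

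The damage is therefore serious for a fairly common event with poor capture, and small for a rarer event with moderate capture.

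**The case against.** The strongest objection is that the low bias is not demonstrated. No passage says how often silent subsidence or migration goes uncharted. The severity scale includes a grade for events without symptoms, so the log can accept them. Source documents include X-rays, the monitor checks forms against source, and inconsistent entries are queried. The general form instructions also allow N/D for something not done or not asked. All of this is true, but none of it requires anyone to re-read the films for these events, and any look by the site would not be independent. The gap stands; its size is unknown.

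The literature comparison could also be distorted the other way. The plan does not say whether the published rates were chart-based or film-based, and a reader-based rate set against chart-based comparators would be its own mismatch. This stands, and the fix allows for it.

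A reader might infer that the reader-based rate should replace the charted one. The documents do not support that. Events treated before 12 months may not show on the final film. Some patients will lack one or both films: they are collected as available, and the plan allows for up to 15% without 12-month data. Used alone, reader rates could be lower than charted rates.

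A reader might also infer that the readers already hold every film, or that reduced subsidence is a claim under test. The forms only ask whether a disc was provided. Section 1.1 speaks of a possibility for a class of designs, and the hypothesis does not mention subsidence. Nor is component fracture purely an imaging finding, since it also appears on the intra-operative log.

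**Conclusion.** The point holds as a weakness in how events are ascertained. In the visible text, the listed imaging-type events come only from site chart abstraction, chart silence is counted as No, and the independent readers are asked for nothing but fusion grades. The reported rates may therefore be too low.

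The direction is a reasoned inference, and the size is not in the documents. With an assumed true rate of 10% in 100 patients, only the 30% capture case gives an expected-count interval that excludes the truth. The statement that a 1.6% event will be seen with 80% probability needs full capture, and drops to about 55% if half of events are charted. It would go too far to say that the rates are known to be biased, or by how much.

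Some text was not available for this review, including what stands under section 8 (Personnel/Equipment), and the monitoring and data-processing plans are separate documents. The conclusion is limited accordingly. The change is worth making because it is cheap and concerns a stated secondary outcome.

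**What to change.** 1. Add per-level fields to the Radiographic Reviewer form for subsidence, migration or retropulsion, loss of expansion, component fracture and loss of fixation. Each takes yes, no or not assessable, with a definition fixed before reading starts. Add a second X-ray date so that the intra-operative and 12-month films can be read as a pair.
2. Use the existing readers and the same route for settling disagreements.
3. Report three rates for each event: site-charted (all included patients), reader-detected (patients with assessable films, denominator stated) and combined (either source). The combined rate keeps events treated before 12 months.
4. For each literature comparison, state whether the comparator was chart-based or film-based.
5. Rename the log item as clinically diagnosed non-union, report it separately from reader grades 3-4, and cross-tabulate the two.

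The cost is a revised form page, agreed definitions, longer reads with some adjudication, and an added table. No new films, readers or patients are needed. Some film pairs will not be assessable, and the event rates may look less favourable.
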